4.4.2 Prohibited Therapy

Any concomitant therapy intended for the treatment of cancer, whether health authority-approved or experimental, unless otherwise specified, is prohibited. This includes but is not limited to the following:

- Chemotherapy, hormonal therapy, immunotherapy, radiotherapy, or investigational agents (except for maintenance therapies outlined in Sections [4.1.1](#) and [4.1.2](#))

- After completion of Cycle 1, certain forms of radiotherapy may be considered for palliation if patients are deriving benefit (e.g., treatment of known bone metastases)
- Patients experiencing a mixed response requiring local therapy (e.g., surgery, stereotactic radiosurgery, radiotherapy, radiofrequency ablation) for control of three or fewer lesions may still be eligible to continue study treatment. Patients who receive local therapy directed at a target lesion will no longer be evaluable for radiographic response but will remain evaluable for progression. Such cases must be discussed with and approved by the Sponsor
- Patients should not receive abatacept or belatacept treatment (those who were receiving it must stop it > 8 weeks before study entry)

Patients are not allowed to receive immunostimulatory agents, including but not limited to interferon (IFN)- α , IFN- γ , or IL-2, during the entire study. These agents, in combination with atezolizumab, could potentially increase the risk for autoimmune conditions.

Systemic corticosteroids, immunosuppressive medications, and anti-TNF- α agents may attenuate potential beneficial immunologic effects of treatment with atezolizumab, but may be administered at the discretion of the treating physician after consultation with the Medical Monitor. If feasible, alternatives to these agents should be considered.

Patients with CNS metastases are allowed to receive anticonvulsants and steroid treatments if the dose of prednisone is stable and \leq 20 mg/day (or equivalent).

The above list of medications is not necessarily comprehensive. The investigator should consult the prescribing information for any concomitant medication and contact the Medical Monitor if questions arise regarding medications not listed above.

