4.5.6 Ongoing Tumor Assessments

Patients who discontinue study treatment early for reasons other than disease progression (e.g., toxicity) should continue to undergo scheduled tumor assessments (See [Appendix 1](#)) until the patient dies, experiences confirmed disease progression, withdraws consent, until study termination, or until the study closes, whichever occurs first.

Patients who start a new anti-cancer therapy in the absence of disease progression should continue to be followed for progression according to the protocol schedule of response assessments, unless consent is withdrawn or the patient experiences disease progression or death or until study termination or withdrawal from study, whichever occurs first.

In those patients for whom tumor assessments are performed as part of local clinical practice and are available for report after PD or atezolizumab treatment discontinuation, overall response rate (ORR) and progression-free survival (PFS) will be assessed from the first date of the new anticancer therapy to the end of the study. These data will be used in an exploratory fashion to assess whether prior atezolizumab treatment positively influences response to subsequent anticancer therapies.

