4.6.2 Study Treatment Discontinuation

Patients must discontinue study treatment (but will continue to receive tumor assessments) if they experience any of the following:

- Intolerable toxicity related to study treatment
- Myocarditis of any grade
- Any medical condition that may jeopardize the patient's safety if he or she continues on study treatment
- Use of another systemic anti-cancer therapy (see Section [4.4.2](#))
- Pregnancy
- Radiographic disease progression per RECIST v1.1

[figure not shown]
Exception: Patients will be permitted to continue atezolizumab after RECIST v1.1 criteria for progressive disease are met if they meet all of the following criteria (see [Figure 3](#) for schematic representation):

- Evidence of clinical benefit (defined as the stabilization or improvement of disease-related symptoms) as assessed by the investigator
- Absence of symptoms and signs (including worsening of laboratory values [e.g., new or worsening hypercalcemia]) indicating unequivocal progression of disease
- No decline in ECOG performance status that can be attributed to disease progression
- Absence of tumor progression at critical anatomical sites (e.g., leptomeningeal disease) that cannot be readily managed and stabilized by protocol-allowed medical interventions prior to repeat dosing

Patients who demonstrate confirmed radiographic disease progression may be considered for continued study treatment at the discretion of the investigator, provided they continue to meet all the criteria above

The primary reason for study treatment discontinuation should be documented on the appropriate eCRF. Patients who discontinue study treatment prematurely will not be replaced.

Figure 3 Conditions for Continuing Atezolizumab in the Presence of Increased Radiographic Tumor Size

ECOG PS, Eastern Cooperative Oncology Group performance status; ICF, Informed Consent Form; RECIST v1.1, Response Evaluation Criteria in Solid Tumors, Version 1.1.

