- l. Urinalysis includes specific gravity, pH, glucose, protein, ketones, and blood.
- m. A serum pregnancy test (for women of childbearing potential, including women who have had a tubal ligation) must be performed and documented as negative within 14 days prior to Day 1. On study pregnancy tests performed every 3 treatment cycles can be conducted with serum or urine.
- n. The same radiographic procedure should be used throughout the study for each patient. A CT (with contrast) or MRI of the head must be included in screening tumor assessments for patients with known or suspected CNS disease. Results must be reviewed by the investigator before dosing at the next cycle. Patients who continue treatment beyond radiographic disease progression assessed per RECIST v1.1 should be monitored with a follow-up scan at the next scheduled tumor assessment when the scan frequency is every 6 weeks, and will be assessed

Appendix 1

Schedule of Assessments (cont.)

by modified RECIST criteria (see [Appendix 3](#)) until treatment discontinuation. If the scan frequency is every 9 weeks, a follow-up scan is recommended at 9 weeks or earlier if clinically indicated. Investigators may perform additional scans or more frequent assessments if clinically indicated.

- o. Ideally within 14 days of the start of study treatment.
- p. Patients will undergo tumor assessments at baseline, every 6 weeks \pm 5 days for the first 48 weeks following treatment initiation, and every 9 weeks thereafter until radiographic disease progression per RECIST v1.1 or (for patients who continue atezolizumab after radiographic disease progression) loss of clinical benefit as determined by the investigator (see Section [4.6.2](#) for details). Thus, tumor assessments are to continue according to schedule in patients who discontinue treatment for reasons other than disease progression or loss of clinical benefit, even if they start new anti-cancer therapy.
- q. For sites where EGFR/ALK testing is not routinely performed at local laboratories, a minimum of 7 consecutively cut slides from a most recent FFPE tumor tissue block must be submitted for EGFR/ALK testing for all patients with non-squamous NSCLC. Testing is not required for patients who have squamous NSCLC. EGFR mutation and ALK testing should be considered for patients with squamous NSCLC who are never-smokers, have mixed histology or small biopsy specimen.

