^a When lymph nodes are included as target lesions, the % change in the sum of the diameters may not be 100% even if complete response criteria are met since a normal lymph node is defined as having a short axis of < 10 mm. Any pathological lymph nodes (whether target or non-target) must have reduction in short axis to < 10 mm in order to meet the definition of CR.

BEST OVERALL RESPONSE: ALL TIMEPOINTS

The best overall response is determined once all the data for the patient are known.

Appendix 3

Modified Response Evaluation Criteria in Solid Tumors (cont.)

The best overall response according to modified RECIST is interpreted as below:

- **CR:** Complete disappearance of all tumor lesions (target and non-target) and no new measurable or unmeasurable lesions, confirmed by a consecutive assessment \geq 4 weeks from the date first documented. All lymph nodes short axes must be < 10 mm.
- **PR:** Decrease in the sum of the diameters of all target and all new measurable lesions $\geq 30\%$ relative to baseline, in the absence of CR, confirmed by a consecutive assessment \geq 4 weeks from the date first documented.
- **SD:** Criteria for CR, PR, and PD are not met.
- **PD:** Increase in the sum of the diameters of all target and all new measurable lesions $\geq 20\%$ relative to the nadir, which may be confirmed by a consecutive assessment \geq 4 weeks from the date first documented as follows:

The confirmatory assessment shows an additional measurable increase in tumor burden as measured by the sum of the diameters of all target and all new measurable lesions.

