3.3 ANALYSIS OF TREATMENT GROUP

The following analyses will be based on the Safety population.

Demographic characteristics, such as age, sex, race, ethnicity, and baseline disease characteristics, such as histology subtype, ECOG performance status, tobacco use history, number of prior cancer treatments, history of autoimmune disease and serology values will be summarized for the Safety population using means, standard deviations (SDs), medians, ranges and inter-quartile ranges for continuous variables and frequencies and percentages for categorical variables, as appropriate.

The baseline value will be defined as the last available value recorded on or prior to the first administration of any study medication.

Lung cancer history (including PD-L1 expression from local and/or central labs), CNS metastasis at baseline and details on the tumor metastasis at baseline and organs involved will also be summarized.

Prior and concurrent medical history, including but not limited to prior anti-cancer surgery, prior lines of NSCLC therapy, prior cancer immunotherapy, prior radiotherapy, prior TKI therapy, systemic therapy and medications will be summarized overall.

Subsequent anti-cancer therapies administered after progression, anti-cancer therapies administered before progression or for patients with no progression, follow-up cancer radiotherapy, on-study radiotherapy, on-study and follow-up cancer-related medical/surgical procedures will be summarized overall.

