3.4.1.3 Best Overall Response

BOR according to RECIST v1.1, for a subject is defined as the most favorable outcome, at any visit after the start date of study treatment and up to the first documented disease progression per RECIST v1.1. Confirmation of response according to RECIST v1.1 is required.

A minimum interval of 6 weeks (42 days) will be considered for Stable Disease (SD) to be assigned as best overall response, i.e. in the case the single response is SD, PR or CR, this single response must have been assessed no less than 6 weeks (at least 42 days) after start date of study treatment.

A patient is assigned a BOR of PD if he has a response assessment of PD at any visit, and not a BOR of CR, PR, or SD otherwise the best overall response will be Non-Evaluable (NE).

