3.4.1.5 Duration of Response

DOOR according to RECIST 1.1 is defined as the time from the first tumor assessment that supports the patient's objective response (CR or PR, whichever is first reported) to documented disease progression as determined by the investigator according to RECIST v1.1 or death from any cause, whichever occurs first, among patients who have a best overall response as CR or PR.

Patients who are alive and have not experienced disease progression at the time of clinical cut-off date will be censored at the time of the last tumor assessment date. If no tumor assessments were performed after the date of the first occurrence of a CR or PR, DOOR will be censored at the date of the first occurrence of a CR or PR plus 1 day.

3.4.1.6 Objective Response Rate, Progression Free Survival, and Duration of Objective Response per Modified RECIST

ORR, PFS, and DOOR analyses using modified RECIST criteria. The investigator-assessed ORR is defined as the proportion of patients whose confirmed best overall response is either a PR or CR per modified RECIST. An estimate of ORR and its 95% CI will be calculated for the ITT population using the Clopper-Pearson method.

For patients experienced an objective response (CR or PR per modified RECIST) during the study as assessed by the investigator, DOOR is defined as the duration from the first tumor assessment that supports the patient's objective response (CR or PR, whichever is first recorded) to disease progression or death due to any cause, whichever occurs first.

Patients who are alive and who have not experienced disease progression at the time of analysis will be censored at the last tumor assessment date. DOOR will be assessed using Kaplan-Meier methodology.

PFS by modified RECIST is defined as the time from first treatment taken to disease progression as determined by the investigator per modified RECIST or death from any cause, whichever occurs first. A patient is considered to have disease progression by modified RECIST if either of the following conditions were met:

- a) Modified RECIST criteria for progression were met at a tumor assessment and no subsequent tumor assessment was performed.
- b) Modified RECIST criteria for progression were met at a tumor assessment, and at the subsequent tumor assessment, the criteria for confirmed progression by modified RECIST were also met.

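### Atezolizumab response is not cut off at the start of new anti-cancer therapy, and next-line PFS is censored at last contact alive although next-line scans after progression are not mandated

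*SAP*

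**What the plan says.** **Response window.** SAP 3.4.1.3 defines best overall response under RECIST v1.1 as the best result recorded "at any visit after the start date of study treatment and up to the first documented disease progression per RECIST v1.1". SAP 3.4.1.4 builds ORR on it. For modified RECIST, SAP 3.4.1.6 says "The investigator-assessed ORR is defined as the proportion of patients whose confirmed best overall response is either a PR or CR per modified RECIST", and Protocol Appendix 3 adds "The best overall response is determined once all the data for the patient are known". None of these stops at the start of new anti-cancer therapy.

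**Scanning after a switch.** Protocol 4.6.2 lists use of another systemic anti-cancer therapy under the rule "Patients must discontinue study treatment (but will continue to receive tumor assessments) if they experience any of the following". Protocol 4.5.6 says "Patients who start a new anti-cancer therapy in the absence of disease progression should continue to be followed for progression", and Appendix 1, footnote p, keeps scans on schedule "even if they start new anti-cancer therapy". SAP 3.3 plans a summary of "anti-cancer therapies administered before progression or for patients with no progression", so such patients are expected.

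**A split already in the protocol.** Section 4.4.2: "Patients who receive local therapy directed at a target lesion will no longer be evaluable for radiographic response but will remain evaluable for progression".

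**Next-line endpoints.** SAP 3.4.3.1 (next-line PFS) and 3.4.3.3 (PFS2) censor living, progression-free patients at the last date known alive. Main PFS (SAP 3.4.1.2) censors at the last tumor assessment. Protocol 3.1 and 4.5.6, and the synopsis in SAP Appendix 1, confine next-line response and PFS to patients whose locally performed scans are available. Protocol 6.6.3 and SAP 3.4.3.1 describe everyone who started new therapy. SAP section 3 says the SAP supersedes the protocol.

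**The concern.** A patient who leaves atezolizumab without progression, starts another drug and first responds on that drug is a responder to atezolizumab under the written rule. The same response enters the DOR responder set and counts again in next-line ORR (SAP 3.4.3.2). The ORR denominator is fixed, so the error has one direction only. ORR is a secondary endpoint that will be read as atezolizumab activity.

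For next-line PFS, an unscanned living patient counts as progression-free for as long as survival contact continues. In SAP 3.4.3.2 the same patient counts as a non-responder. Missing scans would therefore push next-line PFS up and next-line ORR down, for reasons unrelated to treatment. These endpoints have no comparator to absorb the distortion. PFS2 shares the censoring rule and the direction of bias.

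**Working it through.** The plan states no figure for these endpoints, so there is none to reproduce. The share switching before progression and the share never scanned on next-line therapy are not in the documents. Both are assumed over a range.

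**1. ORR**

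Inputs:
- N = 600.
- Base ORR 14% (Protocol 1.2.1.4, OAK ITT, atezolizumab arm).
- Next-line response rate r from 8.8% (docetaxel, low end) to 23% (ramucirumab + docetaxel), Protocol Table 3.
- Share f switching before progression, assumed 5-10%.

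Only patients not already responding can be added, so ORR read = 0.14 + f × 0.86 × r.

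| f | r | ORR read | Extra responders of 600 |
|---|---|---|---|
| 0.05 | 0.088 | 14.4% | 2.3 |
| 0.05 | 0.23 | 15.0% | 5.9 |
| 0.10 | 0.088 | 14.8% | 4.5 |
| 0.10 | 0.23 | 16.0% | 11.9 |

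The Clopper-Pearson interval for 84/600 is 11.3-17.0%. The table is an upper range, because a credited response must be confirmed and must reach a 30% decrease from the baseline taken before atezolizumab. If half qualify, ORR reads 14.2-15.0%.

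**2. Next-line PFS under the current rule**

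Let u be the unscanned share, hd = ln2 / (OS median) and hp = ln2 / (PFS median) − hd. Unscanned patients have an event only at death, so the median t solves

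(1−u)·exp(−(hp+hd)t) + u·exp(−hd·t) = 0.5.

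Docetaxel medians are used as illustrations (Protocol Tables 3 and 6).

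| PFS / OS median (months) | u = 0.25 | u = 0.50 | u = 0.75 |
|---|---|---|---|
| 2.9 / 7.9 | 3.59 | 4.61 | 6.05 |
| 4.2 / 9.4 | 5.02 | 6.13 | 7.59 |

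Check of the first row at u = 0.50: hd = 0.0877 and hp + hd = 0.2390. At t = 4.61, 0.5 × 0.332 + 0.5 × 0.667 = 0.50.

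A simulation with 6-weekly scans and OS 8.3 months (the POPLAR figure in Protocol 3.3.6) gives the same direction. A median of 3.3 months under complete scanning reads 4.1 at 25% unscanned and 5.4 at 50%. With nobody wholly unscanned but scans stopping after a mean of 6 months, 3.3 still reads 4.1.

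**3. Next-line ORR**

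0.23 × (1−u) = 17.3%, 11.5% and 5.8% at u = 0.25, 0.50 and 0.75.

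**4. Effect of censoring at the last scan**

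Living unscanned patients are censored at day 1 and deaths are kept as events (400,000 simulated patients).

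| Cut-off (months, uniform) | True median | u = 0.25 | u = 0.50 | u = 0.75 |
|---|---|---|---|---|
| 6-36 | 2.9 | 3.32 | 3.91 | 4.71 |
| 6-36 | 4.2 | 4.58 | 5.02 | 5.59 |
| 0-18 | 2.9 | 3.00 | 3.16 | 3.37 |
| 0-18 | 4.2 | 4.15 | 4.09 | 4.00 |

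With the 6-36 month cut-off and u = 0.50, the share of bias removed is (4.61−3.91)/(4.61−2.9) = 41% and (6.13−5.02)/(6.13−4.2) = 58%. With short follow-up the rule can slightly overcorrect.

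**The case against.** - **Modified RECIST may already be bounded.** Protocol 4.5.5 applies it until treatment is discontinued, and another systemic therapy forces discontinuation. But that sentence concerns patients treated beyond progression, not those who switch without it, and it does not bound RECIST v1.1.
- **The study schema gives next-line response its own window.** Footnote c starts it at the first date of new therapy. That opens a second window without closing the first, which is how the double counting arises.
- **The inputs are assumed and the ORR effect is small.** This stands. No switching share is given, the response rates come from other second-line settings, and the result stays inside sampling error in a descriptive study.
- **Main PFS and DOR also run through new therapy, so the SAP is consistent.** That is a fair argument for leaving progression follow-up alone. It does not justify crediting a response to a drug the patient has stopped. Local therapy differs from systemic therapy in how it affects measurement, so Protocol 4.4.2 is a precedent for the split, not an exact parallel.
- **The SAP's own synopsis limits next-line analyses to available scans.** If that governs, the unscanned-patient scenarios do not arise. SAP 3.4.3.1 says otherwise, so the conflict needs resolving. Bias can persist where scans stop early.
- **Progression might be taken from medical records.** If so, the next-line figures shrink. They assume that unscanned progression goes unreported.
- **The censoring change is only a partial cure and leaves PFS2 alone.** Both are true, and the fix says so.

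**Conclusion.** The concern holds, as a point to consider rather than a threat to the trial's primary safety result. The written response window credits next-line responses to atezolizumab. The direction is certain. The size is at most about 0.4 to 2.0 percentage points if 5-10% switch before progression, and less once confirmation and depth of response are required.

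The next-line PFS rule is biased upward if unscanned patients are included and their progression is not otherwise reported. At 50% unscanned, the median rises by about 1.7 months (2.9 to 4.6) or 1.9 months (4.2 to 6.1) under exponential models with assumed docetaxel medians. Next-line ORR falls in proportion to the unscanned share. For PFS2 only the upward direction is established.

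**What to change.** 1. **Response.** Determine best overall response and ORR, under both RECIST v1.1 and modified RECIST, from assessments up to the earlier of progression or start of new systemic anti-cancer therapy. The DOR responder set follows. Keep the current window as a sensitivity analysis. Follow-up for DOR after a valid response can stay aligned with main PFS.
2. **Next-line population and censoring.** State one population, reconciling Protocol 3.1, 4.5.6 and SAP Appendix 1 with Protocol 6.6.3 and SAP 3.4.3.1. Censor next-line PFS at the last tumor assessment without next-line progression, or at the start of new therapy plus 1 day if there is none. Keep deaths as events and the current rule as a sensitivity analysis. State that this reduces the bias without removing it.
3. **Reporting.** Give the number of next-line patients with no scan alongside next-line PFS, next-line ORR and PFS2. State that missing next-line scans bias PFS2 upward; its censoring need not change.

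The cost is a few SAP sentences and minor programming, with no new data. ORR may fall slightly, next-line PFS loses some follow-up, and some bias remains.

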3.4.1.4 Objective Response Rate

ORR, according to RECIST v1.1, is defined as the proportion of patients with a confirmed BOR, either CR or PR, as determined by the investigator using RECIST v1.1. Patients not meeting this criterion, including those without any post-baseline assessment, will be considered non-responders.

An estimate of ORR and its 95% CI will be calculated using the Clopper-Pearson method.

3.4.1.5 Duration of Response

DOOR according to RECIST 1.1 is defined as the time from the first tumor assessment that supports the patient's objective response (CR or PR, whichever is first reported) to documented disease progression as determined by the investigator according to RECIST v1.1 or death from any cause, whichever occurs first, among patients who have a best overall response as CR or PR.

Patients who are alive and have not experienced disease progression at the time of clinical cut-off date will be censored at the time of the last tumor assessment date. If no tumor assessments were performed after the date of the first occurrence of a CR or PR, DOOR will be censored at the date of the first occurrence of a CR or PR plus 1 day.

3.4.1.6 Objective Response Rate, Progression Free Survival, and Duration of Objective Response per Modified RECIST

ORR, PFS, and DOOR analyses using modified RECIST criteria. The investigator-assessed ORR is defined as the proportion of patients whose confirmed best overall response is either a PR or CR per modified RECIST. An estimate of ORR and its 95% CI will be calculated for the ITT population using the Clopper-Pearson method.

For patients experienced an objective response (CR or PR per modified RECIST) during the study as assessed by the investigator, DOOR is defined as the duration from the first tumor assessment that supports the patient's objective response (CR or PR, whichever is first recorded) to disease progression or death due to any cause, whichever occurs first.

Patients who are alive and who have not experienced disease progression at the time of analysis will be censored at the last tumor assessment date. DOOR will be assessed using Kaplan-Meier methodology.

PFS by modified RECIST is defined as the time from first treatment taken to disease progression as determined by the investigator per modified RECIST or death from any cause, whichever occurs first. A patient is considered to have disease progression by modified RECIST if either of the following conditions were met:

- a) Modified RECIST criteria for progression were met at a tumor assessment and no subsequent tumor assessment was performed.
- b) Modified RECIST criteria for progression were met at a tumor assessment, and at the subsequent tumor assessment, the criteria for confirmed progression by modified RECIST were also met.

For patients who meet criterion a, the date of progression is the date of the tumor assessment that met the criteria for modified RECIST. For patients who meet criterion b, the date of progression is the date of the tumor assessment at which the modified RECIST criteria for progression were first met. Patients who did not meet either of the above criteria are not considered to have had disease progression by modified RECIST.

PFS and DOR per modified RECIST will be summarized using the Kaplan-Meier methodology.

